# 12.1 Adverse event recording

Adverse events are registered either on the basis of complaints spontaneously reported by the patient or by the Investigator interviewing the patient or using physical examination findings and results of laboratory and instrumental investigations. The investigator should formulate his / her questions to the patient so that they do not prompt the patient to report unreliable information.

Adverse events should be registered in respective sections of the CRF, as well as in the patient's source medical documents.

Serious AEs are recorded from the time of signing the informed consent to participate in the study. All other adverse events will be registered beginning from the first dose of the investigational medicinal product. Adverse events will be registered until the end of the follow-up period. Reporting of serious AEs is described in section 12.5.

The following information should be reported for a registered adverse event:

- Patient ID
- Diagnosis of the adverse event (a diagnosis should be preferred to listing symptoms)
- The onset and resolution dates for the adverse event (and the times if applicable)
- AE severity
- Study drug relationship
- The measures that have been taken due to the adverse manifestation
- Actions taken in relation to the investigational drug
- Whether the adverse event meets the serious adverse event criteria

Adverse event outcome

CONFIDENTIAL P. 67 of 84

# 12.2 Causality assessment between the adverse event and the use of the investigational product

To evaluate the causal relationship with the use of the investigational product, all available information should be taken into consideration if it can help characterize this relationship, in particular the mechanism of action of the investigational product, information about known adverse effects of the product from the Investigator's Brochure, characteristics of the adverse event, temporal relationship between the adverse event and the use of the study drug, time to resolution of the adverse event, and other possible causes of the adverse event, which may include the following:

- Use of other medications or exposure to chemical substances
- The natural course of the primary disease or other conditions
- Study procedures
- Other factors

The Investigator should determine the causal relationship for the adverse event using the definitions below:

- Unlikely: an adverse event is temporally related to the administration of the investigational product, but there are some other factors (such as a concomitant disease or an effect of other medications, chemical or physical factors) that appear to be more plausible causes of this adverse event;
- **Possible:** an adverse event is temporally related to the administration of the investigational product, but its development may also be explained by other factors (such as a concomitant disease or an effect of other medications, chemical or physical factors);
- **Probable:** an adverse event is temporally related to the administration of the investigational product. The causal relationship with other factors (such as a concomitant disease or an effect of other medications, chemical or physical factors) appears unlikely; The adverse event regresses after discontinuation of the investigational product;
- Certain: an adverse event is temporally related to the administration of the investigational product. The adverse event cannot be explained by other factors (such as a concomitant disease or an effect of other medications, chemical or physical factors); the adverse event regresses after discontinuation of the investigational product. The adverse event recurs after rechallenge;
- Unrelated: no relationship with the medicinal product: in the presence of an apparent alternative explanation and/or an unsubstantiated temporal relationship between the medicinal product and the event, and/or in the event when the relationship is biologically implausible.

If the assessed relationship changes over time as a result of new or changed information, it may be revised.

CONFIDENTIAL P. 68 of 84

# 12.3 Adverse event severity

The investigator assesses the severity of all AEs reported during the study based on the following categories:

Mild: The study participant tolerates the AE well, with minimal discomfort, does

not interfere with normal daily activities.

Moderate: The event causes significant discomfort and interferes with daily activities.

Severe: The event does not allow carrying out daily activities.

In accordance with the standard healthcare practice in the Russian Federation, the following interpretation of AE severity by grade, used in the study, is considered correct:

Mild corresponds to CTCAE v 5.0 Grade 1,

Moderate corresponds to CTCAE v 5.0 Grade 2 and Grade 3,

Severe corresponds to CTCAE v 5.0 Grade 4 and Grade 5

A severe AE should not be confused with a serious AE. Severity is a category for assessing the intensity of an event, both non-serious AEs and serious AEs can be severe. A serious adverse event is an event that meets at least one of the criteria specified in the definition of a Serious Adverse Event (see 12.4).

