#### 12 ADVERSE EVENTS

In this study, an **adverse event** (AE) means any untoward medical event in a patient receiving the study drug that does not necessarily have a causal relationship with the drug. Thus, an adverse event can be any unintended and untoward symptom (for example, a laboratory abnormality), a symptom or a disease with temporal relationship with the use of the drug, regardless of whether they are considered to be related with the drug.

Clinical signs of treatment failure are not adverse events. For example, persistent pain or swelling in an affected joint should not be reported as an adverse event.

Symptoms, syndromes, and diseases noted prior to the study therapy, but after the patient signed the informed consent form, are recorded in the CRF as Concomitant Diseases.

Laboratory and investigation abnormalities should be registered as adverse events if these abnormalities are regarded by the investigator as clinically significant.

An **adverse drug reaction** is any adverse event with at least a possible (possible, probable, or certain) relationship with the use of the investigational medicinal product.

AE severity is graded according to the CTCAE classification v.5.0.

All adverse events should be monitored until resolution or stabilization (assessed by the investigator).

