#### 13.6.1 Adverse events

Adverse events occurring starting from the time of investigational product administration (start of use) until 45 days after the investigational product administration will be considered treatment-emergent adverse events.

Serious adverse events developing between the signing by the patient of the Informed Consent Form for participation in this study and the administration of the investigational medicinal product will be regarded as pre-treatment SAEs.

Adverse event data will be coded using the last version of the MedDRA medical terminology. Frequency rates of adverse events during the study therapy will be calculated for each organ system, by primary diagnosis, investigational product dose, and absolute and relative amounts of patients developing adverse events. Summary data reflecting the severity of adverse events will be presented by organ system and primary disease. Adverse events related to the investigational product ('possibly related,' 'probably related,' and 'definitely related') will be presented separately.

Summary data reflecting withdrawals from the study due to adverse events will be presented by organ system and primary disease.

Serious adverse event data will be presented as listings and summary data by organ system and primary disease.

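### The plan names two adverse event severity scales without saying which is recorded or tabulated; under the section 12.3 categories, Grade 3 events count as moderate and cannot be told from Grade 2

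*Combined protocol and SAP*

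**What the plan says.** The opening of section 12 sets the instrument: "AE severity is graded according to the CTCAE classification v.5.0". Section 12.3 then gives a different procedure: "The investigator assesses the severity of all AEs reported during the study based on the following categories", followed by mild, moderate and severe defined by discomfort and interference with ordinary life. Severe is defined as: "The event does not allow carrying out daily activities".

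Section 12.3 next links the two scales. Citing standard practice in the Russian Federation, it states that "the following interpretation of AE severity by grade, used in the study, is considered correct". The map itself has three lines. The first makes Grade 1 mild. The second, on which this point turns, reads "Moderate corresponds to CTCAE v 5.0 Grade 2 and Grade 3". The third reserves the label severe for Grades 4 and 5.

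Section 12.1 lists severity among the items to report for each adverse event, without naming a scale. Section 13.6.1 plans the output: "Summary data reflecting the severity of adverse events will be presented by organ system and primary disease". It does not name a scale either. Section 13.1.7 leaves further analysis detail to a separate statistical analysis plan, to be approved before the data lock point for the interim analysis. That plan is not in the supplied text.

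**The concern.** One data item is governed by two rules, and nothing says which is entered in the CRF or which reaches the tables. The choice matters because the map is coarse where a safety reader most wants detail: it places the boundary of severe above Grade 3.

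Section 6.1.5 names the frequency and severity of adverse events as safety variables. Section 4.4 states the safety expectation in the same vocabulary: single doses up to 160 mg are not expected to cause severe reactions. Under the map a Grade 3 reaction is labelled moderate and would not count against that expectation. A summary showing no severe events could therefore be read as reassurance that the data behind it do not give.

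**Working it through.** The plan states no figure on this point, so the check sets the sections side by side and follows the logic of the map.

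**Step 1. What is recorded?** Section 12 points to a grade from 1 to 5. Section 12.3 points to one of three categories assigned directly by the investigator. Section 12.1 asks only for severity. Both readings fit the text.

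**Step 2. What is tabulated?** Section 13.6.1 says only severity. Again, both readings fit.

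**Step 3. What does each combination show?**

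| Recorded | Tabulated | Is Grade 3 visible? |
|---|---|---|
| Grade 1 to 5 | Grade 1 to 5 | Yes |
| Grade 1 to 5 | Three categories | Not in the table; recoverable from listings |
| Three categories | Three categories | No; lost at data capture |

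**Step 4. What can be said about Grade 3 or above from a three-category table?** With the map, mild = {1}, moderate = {2, 3} and severe = {4, 5}. Then

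n(Grade ≥3) = n(Grade 3) + n(severe), with 0 ≤ n(Grade 3) ≤ n(moderate),

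so

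n(severe) ≤ n(Grade ≥3) ≤ n(moderate) + n(severe).

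The width of the interval is n(moderate). The same bound holds for patients classified by their worst event. It assumes that the map is applied. If investigators rate by the functional definitions alone, the grade content of each category is not fixed, and even this bound is not assured.

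**Step 5. Illustration in the planned arms.** Suppose one patient in an arm of 14 has one Grade 3 event and there are no other moderate or severe events. The true rate at Grade 3 or above is 1/14 = 7.1%. The table shows 0/14 = 0% severe and 1/14 moderate. The bound runs from 0 to 1 patient, or 0% to 7.1%.

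**Step 6. Illustration at the interim analysis.** Section 4 says that the report on 47 patients may become final. Arm sizes at that point are not given. Assume that Period 1 filled at 22 patients and that the rest were allocated 2:2:2:2:1. Then 47 − 22 = 25, and each higher-dose arm has 25 × 2/9 = 5.6, so about 5 or 6 patients. One Grade 3 event would be 1/6 = 17% to 1/5 = 20% of such an arm, again shown as 0% severe.

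**The case against.** A reader might infer that the severity tables cannot show Grade 3 events at all, or that every Grade 3 event will be tabulated as moderate. The documents do not support that. Section 12 calls for CTCAE grading, section 13.6.1 does not commit to the three categories, section 13.1 lists all individual values, and the separate analysis plan may set a table by grade. This objection stands, and it makes the consequence conditional.

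A reader might also infer that the functional definitions and the map contradict each other, since an event that prevents daily activities is severe by definition but moderate by the map if it is Grade 3. The CTCAE criteria are not reproduced in the documents, so a conflict is possible but not shown. The map is also a disclosed convention, written down in advance.

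Other outputs give partial cover. Serious events are defined by outcome in section 12.4, whatever their severity label, and section 13.6.1 lists and summarises them. Withdrawals due to adverse events are summarised, and out-of-range laboratory values are flagged in listings (section 13.6.4). These recover only Grade 3 events that are also serious, lead to withdrawal or are laboratory findings. The adverse event listings help only if the grade itself was recorded.

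It would also be wrong to predict that the map will empty the severe column. Section 4.3.3 reports all phase 1 events as mild, so few severe events could be expected under either grouping. Nor does the title's order of aims carry the argument: it names safety first, but section 5.1 names efficacy first and the primary variable is pain change at 72 hours. The case rests on severity being a named safety variable.

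What remains is a stated rule, not just missing detail: section 12.3 declares the map to be the interpretation used in this study.

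**Conclusion.** The point holds in conditional form and should be corrected. Two severity scales are named, and neither the recorded nor the tabulated one is identified. If the section 12.3 categories are recorded or tabulated and the map is followed, Grade 3 events appear as moderate and cannot be separated from Grade 2 in the summaries. The count at Grade 3 or above is then known only within an interval as wide as the moderate count, and a finding of no severe events would not exclude Grade 3 events.

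The percentages above illustrate a single assumed event and are not predictions. The interim figures also rest on the assumed allocation of the 47 patients. If the five grades are recorded and tabulated, nothing is lost and only the wording needs repair. If only three categories were captured, the loss occurs at data entry and a new table cannot undo it.

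**What to change.** - In sections 12.1 and 12.3, state that the CTCAE grade from 1 to 5 is the recorded variable, and reconcile the functional definitions with the map so that one event has one rating.
- In section 13.6.1 and the separate statistical analysis plan, tabulate adverse events by CTCAE grade and arm, with a Grade 3 or higher line per arm. Keep the three-level table as a supplement. The approval step before the interim data lock point is the natural place for this.
- For patients already enrolled, confirm which scale was captured. If it was only the three categories, re-grade from source records where possible; otherwise state in the report that Grade 3 cannot be separated from Grade 2.

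The cost is one extra safety table if grades were captured. Re-grading from source costs more, and is needed only if they were not. No treatment, visit or assessment changes.

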## 12.4 Serious adverse events (SAEs)

A serious adverse event (SAE) is any adverse event that meets one or more of the criteria listed below:

- 1. Resulted in the patient's death
- 2. Is life-threatening
- 3. Requires hospitalization or prolongation of existing hospitalization
- 4. Resulted in persistent or significant disability or incapacity
- 5. Is a congenital anomaly or developmental defect occurring in children born to patients treated with the investigational drug.

In addition, serious adverse events may include other important medical manifestations if the investigator believes, on the basis of his/her medical experience, that this manifestation may result in one of the outcomes described above if no medical intervention is undertaken.

An adverse event is considered to be "life-threatening" if the patient is at an immediate risk of death at the time of the event. This category does not include adverse events, which hypothetically might have caused the patient's death if they were more severe.

# 12.5 SAE reporting procedure

To ensure safety for study subjects in case of any SAE developing after the patient signs the Informed Consent Form and before the end of the study, regardless of the suspected causes of the SAE or the relationship with the use of the investigational product, the SAE should be reported to the study Sponsor within 24 hours after the investigator becomes aware of the SAE.

If a study subject is found to develop a serious adverse event related to the use of the investigational product, it should be reported even if the study has already been completed.

Filling out the serious adverse event reporting form.

SAEs should be reported by sending a scanned copy of the completed Serious Adverse Event Reporting Form in paper format by e-mail to

CONFIDENTIAL P. 69 of 84

[contact].

or by [contact]

The primary contact for any issues related to the safety of the medicinal product is the Head of the Department of Drug Safety at R-Pharm JSC, Candidate of Medical Sciences, [name].

[contact] [name]

Mob. [contact]

[contact]

email: [contact]; [contact]

The Investigator must notify the LEC about SAEs in accordance with the LEC standard operating procedures.

The Study Sponsor must notify the regulatory authorities of the Russian Federation of all suspected unexpected serious adverse reactions within the time frame specified by the Russian law. In the context of notifying regulatory authorities and investigators, suspected unexpected serious adverse reactions will be deemed to be unexpected serious adverse events assessed by the investigator and/or Sponsor to be doubtfully, possibly, probably, or certainly related to the investigational therapy.

# 12.6 Investigator's responsibilities related to reporting of serious adverse events

Reporting suspected unexpected serious adverse reactions (SUSAR).

The sponsor will inform investigators of all suspected unexpected serious adverse reactions recorded during the study. It is the investigator's responsibility to submit appropriate reports to the Local Ethics Committees of healthcare institution.

Submission of other safety reports.

The Investigators will report to the Local Ethics Committees of healthcare institutions on other treatment safety aspects subject to expedited reporting if they affect the benefit-risk ratio for the study therapy or might necessitate significant modification of the study therapy or study methods.

In addition to submitting expedited reports, the Sponsor will annually prepare development safety update reports for RPH-104, containing all new relevant safety information received during the reporting period. These reports will be forwarded to the investigator for submission to the Local Ethics Committees of healthcare institutions once a year.

#### 12.7 Pregnancy

In the event of pregnancy in a female patient participating in the study, the investigational product will have to be immediately discontinued.

Pregnancy is not an adverse event as such, except where there is reason to believe that the use of the investigational product resulted in decreased effectiveness of the contraceptives used.

Information concerning pregnancies in female patients or sex partners of male patients participating in the study should be registered from the signing of the Informed Consent Form to the end of the study.

If a female patient or a female partner of a male patient participating in the study becomes pregnant, the study Sponsor should be notified by filling out the "Pregnancy reporting". A

CONFIDENTIAL P. 70 of 84

pregnancy report should be filled out by an authorized employee of the study site within 24 hours after the pregnancy information is received. Pregnancy cases should be reported by sending a scanned copy of the filled pregnancy reporting form in paper format by e-mail to: [contact].

Collection of pregnancy-related information should continue until the end of the pregnancy. After the end of the pregnancy, the study Sponsor should be informed about the outcome of the pregnancy (miscarriage, elective abortion, delivery of a healthy infant or infant with congenital anomalies or developmental defects). If possible, the newborn health should be monitored until 6 weeks, 6 months, and 12 months of age.

Any complications of pregnancy should be recorded as adverse events or serious adverse events depending on the seriousness criteria.

Congenital anomalies and developmental defects in subjects' children are serious adverse events. Miscarriages should be recorded as serious adverse events. Elective abortions carried out at the woman's discretion, without medical indications for abortion and not associated with complications, are not adverse events.

# 12.8 Actions in emergency situations

Medical equipment and pharmacological therapy.

The study site should have appropriate equipment and drugs necessary for emergency care. Their use (which may be necessary though unlikely) should be recorded in the CRF.

# 12.9 Follow-up of adverse events

All AEs are followed up until they resolve or stabilize.

#### 13 DATA ANALYSIS AND STATISTICAL ANALYSES

## 13.1 General provisions

Standard statistical calculations for continuous data sets will be performed to indicate the number of cases (N), mean value, standard deviation, minimum, median, and maximum. Categorical data will be reflected by the N value and proportion (%). For all registered types of data, all individual patient values will be listed.

#### **13.1.1** Analysis populations

#### Efficacy population

To assess the treatment efficacy, the population of all randomized patients who received at least one dose of the investigational product and who had at least one VAS measurement of the patient's pain intensity in the assessed joint after the start of the investigational product therapy will be used.

# Safety population

The treatment safety population will include all subjects who have received at least one dose of the investigational medicinal product. This population will be used for all treatment safety assessments. The safety analysis of data will be performed based on the actual treatment received by the patients.

#### Pharmacokinetic population

The pharmacokinetic population will include all subjects who have received at least one dose of the investigational product and for whom sufficient data has been accumulated on the blood concentrations of the investigational product to allow pharmacokinetic calculations.

CONFIDENTIAL P. 71 of 84

Pharmacokinetic data obtained for the investigational product will be analyzed in this patient population.

# Pharmacodynamic population

The pharmacodynamic population will consist of all patients who received the investigational product, for whom sufficient data on levels of cytokines, hs-CRP and serum amyloid protein A have been obtained to assess the pharmacodynamic parameters of the investigational products.

#### 13.1.2 Sample size

The study is planned to randomize 85 patients: 15 patients in the RPH-104 4 mg group, and 14 patients in the RPH-104 20 mg, 40 mg, 80 mg and 160 mg groups each, a total of 14 patients in the Voltaren® (diclofenac) group. This sample size will allow constructing 95% confidence intervals around the mean change in pain intensity at 72 hours after the start of the investigational product use in each group with an accuracy of 30 mm change in pain intensity.

In addition, this sample size will allow establishing statistically significant differences between the groups in pairwise comparisons, without control for type I error for multiple comparisons, taking into account the type I error  $\alpha = 5\%$ , if the difference between the compared groups is  $\geq$  20 mm. The sample size was calculated assuming a standard deviation of 26 mm for change in pain intensity at 72 hours [16].

